8. SUBJECT SELECTION AND WITHDRAWAL

I) Inclusion Criteria

1. Diagnosis of Ulcerative Colitis based on the European Crohn's and Colitis Organization criteria.
2. Patients aged 18 years or older.
3. Disease extension of at least left-sided (involvement >25 cm from the anal margin).
4. Moderate flare according to the Mayo Index (score ≥ 6 and ≤ 10).
5. No maintenance treatment or only 5-ASA oral and/or topical treatment.
6. Patient has the capacity to understand study requirements and provide informed consent.
7. Signed Informed Consent.

II) Exclusion Criteria

1. Previous or current treatment with thiopurines, calcineurin inhibitors, methotrexate, and/or biological agents.
2. Systemic corticosteroid use in the last 6 months (excluding topical oral corticosteroids).
3. Severe active or uncontrolled systemic infection, serious diseases, or medical conditions that may interfere with the patient's eligibility or treatment.
4. Uncontrolled diabetes mellitus or hypertension.
5. Psychiatric disorder or any other uncontrolled condition that contraindicates steroid treatment.
6. Pregnancy, lactation, or intention to become pregnant during the study period.
7. History of allergic reactions attributed to corticosteroids.

III) Withdrawal Criteria and Analysis

Premature termination of the trial will occur whenever the clinical trial is terminated before meeting the conditions outlined in the protocol.

Patients may be withdrawn from the study before reaching week 54 (end of follow-up) for any of the following reasons:

- **Patient Decision:** Patients are free to withdraw from the study at any time without any penalty or impact on their disease management or subsequent treatments.
- **Pregnancy.**
- **Serious Complications Due to Steroid Treatment.**
- **Lack of Early Clinical Response.**
- **Failure to Achieve Clinical and Endoscopic Remission, Steroid-Free at Week 8.**
- **Clinical Worsening and Need for Rescue Treatment at the Investigator's Discretion.**
- **Major Protocol Deviation.**

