7. STUDY DESIGN

I) Primary and Secondary Variables

Primary Outcome Variable:

Clinical and endoscopic remission, steroid-free at 8 and 54 weeks, without rescue treatment and without the need for steroids up to week 54.

Secondary Variables (Variables of Interest):

- **Clinical Remission** (assessed at weeks 8 and 54): Mayo Score \leq 2 points with no individual variable $>$ 1.
- **Endoscopic Remission**: Mayo endoscopic subscore of 0 or 1.
- **Clinical Response** (assessed at weeks 8 and 54): a reduction in the Mayo score by at least 3 points and at least 30%, with a decrease in the rectal bleeding subscore of at least 1 point or to an absolute value of 0 or 1.
- **Early Clinical Response**: a decrease in the clinical Mayo subscore by at least 3 points and at least 30%, with a decrease in the rectal bleeding subscore of at least 1 point or to an absolute value of 0 or 1, at days 3 and 7 of corticosteroid treatment.
- **Relapse**: reappearance of symptoms, defined as a Mayo clinical subscore $>$ 2. The time of relapse from treatment initiation will be recorded.
- **Corticosteroid Dependency**: relapse during prednisone tapering or within three months after corticosteroid discontinuation.
- **Rescue Treatment**: restart or increase of the established corticosteroid dose (including topically acting oral corticosteroids) or initiation of any treatment for ulcerative colitis other than mesalazine, including biological agents (infliximab, adalimumab, golimumab, vedolizumab), calcineurin inhibitors (cyclosporine, tacrolimus), thiopurines (azathioprine, mercaptopurine), methotrexate, leukapheresis, or colectomy.
- **Need for Surgery** and time to surgery from treatment initiation.
- **Adverse Event Rate** and rate of severe adverse events (including hospitalizations) recorded throughout the study duration.
- **Fecal Calprotectin Determination**.

II) Study Design

This is a Phase IV, controlled, prospective, randomized, open, multicenter study to compare two corticosteroid treatment regimens for moderate UC flares.

III) Estimated Number of Subjects, Sample Size, and Justification

Study Subjects: Adult patients of both sexes with active moderate ulcerative colitis, with or without maintenance treatment or with oral/topical mesalazine.

Sample Size: 148 patients.

Sample Size Calculation:

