Assuming a probability of clinical and endoscopic remission at 8 weeks and sustained without corticosteroid reintroduction or rescue treatment at 54 weeks of 20% in the control group (oral prednisone), a total of 148 patients are needed to detect a $\geq 20\%$ improvement in the therapeutic group (one-tailed test) with a significance level (α) of 0.05 and a power (β) of 0.20, accounting for an estimated 10% dropout rate.

IV) Randomization and Blinding Techniques

After the patient signs the informed consent document approved by the Research Ethics Committee and AEMPS, and meets all inclusion criteria and none of the exclusion criteria, they will be eligible for inclusion in the trial. Patients will be randomized (1:1) into each treatment arm via a computerized system provided by AEG-RedCap. Randomization will be performed in blocks of 4 and stratified by (1) whether the disease is newly diagnosed, and (2) whether the patient has received maintenance treatment with mesalazine at doses > 2 grams/day in the last three months.

This is an open-label study, meaning both the study subjects and investigators will be aware of the assigned treatment. However, blinding will be maintained in the analysis of blood samples for corticosteroid response predictive factors and calprotectin levels in fecal samples, which will be centralized and blinded. The technician conducting the measurement will not know the treatment arm or the clinical response associated with each sample.

V) Treatment Description

The study medication (methylprednisolone for intravenous bolus) will be supplied by the sponsor, while the oral prednisone, calcium supplements, and aminosalicylates will be supplied as per routine clinical practice.

Treatment Groups:

1. **Intravenous Bolus Group:** 0.5 g/day of methylprednisolone administered intravenously for 3 consecutive days, followed by oral prednisone 60 mg/day for 1 week, with a subsequent tapering regimen (decrease by 10 mg weekly until 20 mg, followed by a decrease of 5 mg weekly until complete withdrawal).
2. **Oral Prednisone Group:** 60 mg/day for 1 week, followed by a tapering regimen (decrease by 10 mg weekly until 20 mg, followed by a decrease of 5 mg weekly until complete withdrawal).

In both groups:

- **Concomitant 5-ASA Suppository Treatment:** 1g/day during the first 4 weeks.
- **Calcium and Vitamin D Supplementation:** Calcium 1000 mg/day and Vitamin D 800 IU/day until corticosteroid withdrawal.

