- **Maintenance Mesalazine Treatment:** Mesalazine 2-2.4 g/day starting from prednisone tapering to 20 mg/day (in patients receiving 5-ASA during the flare-up, it will be discontinued upon inclusion in the study).

- Any other concomitant treatment received by the patient during the study must be recorded in the e-CRD.

Study Procedures: (summarized in Annex 8)

1. Inclusion and exclusion criteria will be reviewed, and informed consent will be signed at Visit 0.
2. Pre-inclusion epidemiological and clinical data will be collected.
3. Anthropometric data: height and weight, taken at the screening visit (V0).
4. Stool sample collection (Clostridium Difficile toxin determination and coproculture) and pregnancy test for women at the screening visit (V0).
5. Vital signs (temperature, heart rate, and blood pressure) and basic physical examination at each visit (V0 to V8).
6. Disease Activity Index according to the Mayo Clinic score (Disease Activity Index – DAI, Annex 2) will be calculated at visits V1, V5, and V8, and clinical subscore will be calculated at all other study visits. Walmsley Index will be calculated at all visits (Annex 3).
7. General laboratory tests (including blood count, renal and liver function, and C-reactive protein) and fecal sample collection for fecal calprotectin determination (samples preserved frozen until study completion for centralized analysis) at each visit.
8. Blood sample collection at baseline for corticosteroid response predictive factors analysis.
9. Rectosigmoidoscopy and Mayo endoscopic subscore calculation (Annex 2) at Visits V0 or V1, V5, and V8.
10. Clinical response assessment at Visits V2 and V3; clinical and endoscopic response assessment at Visits V5 and V8.
11. **Extra Visit for Intravenous Bolus Group (Group 1):** an additional visit on Day 2 (Visit 1.1) for administration of the second corticosteroid bolus.

VI) Recruitment Period, Follow-Up, and Study Duration

- **Patient Inclusion Start Date:** September 2018
- **Patient Inclusion End Date:** September 2020
- **Recruitment Period:** 104 weeks
- **Patient Treatment Duration:** 8 weeks
- **Patient Follow-Up Duration:** 42 weeks
- **Expected Completion Date for Last Enrolled Patient:** September 2021
- **Total Study Duration:** 156 weeks
- **Duration of Patient Participation:** 12 months

VII) Criteria for Premature Study Termination and Interruption

Criteria for Premature Study Termination:

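### Entry rests on a total Mayo score with no minimum endoscopic subscore, so patients already in endoscopic remission by the trial's own definition can be randomised

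*Combined protocol and SAP*

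**What the plan says.** Inclusion criterion 4 (section 8.I) reads "Moderate flare according to the Mayo Index (score ≥ 6 and ≤ 10". The only other criterion on the current state of the bowel is number 3, "Disease extension of at least left-sided (involvement >25 cm from the anal margin", which sets extent and not severity. None of the seven exclusion criteria (section 8.II) mentions endoscopic findings.

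Section 7.I defines endoscopic remission as "Mayo endoscopic subscore of 0 or 1" and clinical remission as a Mayo score of at most 2 with no item above 1. The primary outcome combines them: "Clinical and endoscopic remission, steroid-free at 8 and 54 weeks, without rescue treatment and without the need for steroids up to week 54".

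A baseline endoscopy is already in the schedule (section 7.V, procedure 9): "Rectosigmoidoscopy and Mayo endoscopic subscore calculation (Annex 2) at Visits V0 or V1, V5, and V8". No threshold is attached to the baseline value. Section 7.IV stratifies on new diagnosis and on prior mesalazine dose, not on endoscopic activity. Section 12.I compares the primary outcome with an unadjusted chi-squared test.

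**The concern.** Section 5.II gives the rationale: intravenous steroids are expected to do better, probably because they heal the mucosa in more patients, which should show as more endoscopic remission early on and fewer relapses later. A patient who enters with a subscore of 0 or 1 has nothing to heal on the scale that the trial uses. If that patient is again at 0 or 1 at week 8, the result is counted as endoscopic remission although no healing has been shown.

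Two things are at stake. The first is interpretation. Endoscopic remission is also a listed variable in its own right, and clinical and endoscopic remission at week 8 is an outcome in the predictor analyses of section 12.I. Both would mix induced healing with status at entry. The second is power: if these patients gain less from the boluses than the others, they dilute the difference on the primary outcome.

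**Working it through.** **1. Can such a patient enter?** Annex 2, which holds the Mayo score, is not in the text available, so I assume four items scored 0 to 3. With endoscopic subscore 1, the other three items must sum to 5–9 to give a total of 6–10. With subscore 0 they must sum to 6–9. Both are possible. For example, stool frequency 3, bleeding 1, global assessment 2 and endoscopy 1 total 7. Listing all item profiles with a total of 6–10 gives 145, of which 20 have endoscopy 0 and 32 have endoscopy 1, so 52 in all. These counts show only that the gap exists; they are not patient frequencies. The conclusion needs no more than that the non-endoscopic items can sum to 5.

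**2. What does such a patient already satisfy?** Entry needs a total of at least 6 and clinical remission at most 2, so every patient must improve by at least 4 points. Only the endoscopic component can be satisfied at entry, and it must still be satisfied at weeks 8 and 54.

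**3. The plan's sample size.** Inputs from section 7.III: control success "of 20% in the control group (oral prednisone", a 20-point improvement, one-tailed 5%, power 80% (β = 0.20) and 10% dropout. Section 12 confirms 40% as the expected experimental rate. With p̄ = 0.30:

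n per arm = [1.645·√(2·0.30·0.70) + 0.842·√(0.20·0.80 + 0.40·0.60)]² / 0.20² = 63.9, so 64.

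Then 64/0.90 = 71.1, so 72 per arm and 144 in total, within 3% of the stated 148. Evaluable patients per arm: 148 × 0.90 / 2 = 66.6, taken as 66.

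**4. Power on the plan's assumptions.**

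Power = Φ{[d·√n − 1.645·√(2p̄(1−p̄))] / √(p₁(1−p₁) + p₂(1−p₂))}

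For 20% against 40% with n = 66: (1.625 − 1.066)/0.632 = 0.884, so power is 81.2%.

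**5. Dilution, as an illustration.** Let f be the share entering with subscore 0–1. Keep the control rate at 20% throughout and let the 20-point effect hold in everyone else.

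- No benefit in these patients: p₂ = 0.40 − 0.20f.
- Half the effect (10 points): p₂ = 0.40 − 0.10f.

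Worked case, f = 10% and no benefit: p₂ = 0.38 and d = 0.18, so (1.462 − 1.056)/0.629 = 0.647 and power is 74.1%.

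| f | Difference, no benefit | Power, no benefit | Difference, half effect | Power, half effect |
|---|---|---|---|---|
| 0 | 20 points | 81.2% | 20 points | 81.2% |
| 5% | 19 | 77.8% | 19.5 | 79.5% |
| 10% | 18 | 74.1% | 19 | 77.8% |
| 20% | 16 | 65.9% | 18 | 74.1% |

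If these patients have no benefit but succeed at 40% in both arms instead of 20%, power is about 77%, 73% and 63%.

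**6. Restricting the analysis to subscore 2 or more.** With 66(1 − f) per arm at 20% against 40%, power is 79.3%, 77.4% and 73.0% at f = 5%, 10% and 20%. If the excluded patients have no benefit, this recovers a little under half of the loss. If they have half the effect, it is no better than analysing everyone.

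**The case against.** Starting from the text, a reader might infer three stronger things that the documents do not support.

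- **That these patients have the endoscopic component secured in either arm.** They do not. The subscore must be 0 or 1 at both week 8 and week 54, and it can worsen in a patient in a flare. What holds is narrower: no endoscopic improvement is required.
- **That about a third of patients are affected, from 52 of 145 profiles.** Profiles are not equally likely, and the real share is probably much smaller. The trial enrols a moderate flare with involvement beyond 25 cm, and stool is tested for infection at V0 (section 7.V), although no criterion says how a positive result is handled. These features make a subscore of 0 less plausible without excluding it.
- **That the comparison is biased.** Randomisation balances these patients between arms in expectation.

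The power loss is also open to challenge. It needs f, which is not given, and an assumption about benefit. Section 5.II offers healing only as the probable mechanism, and a patient at subscore 1 could still gain on symptoms, relapse or steroid need. Section 7.III states its rates for the planned population as a whole, so applying the full 20 points only to endoscopically active patients is my reading.

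All of this stands as a limit on size. It does not remove the gap: nothing in the plan requires endoscopic activity at entry, and neither the stratification nor the primary test takes account of it.

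**Conclusion.** The concern holds as one of dilution and interpretability. The entry rule admits patients whose later endoscopic remission cannot be read as induced healing, in a trial whose rationale is healing. It is a weakness of design and not a contradiction or an arithmetical error; the stated sample size reproduces closely.

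The size is unknown because f is unknown. The plan has little slack over its 80% target, so under the no-benefit assumption even f = 5% takes power slightly below it, to about 78%; under half effect it stays at about 80%. Only a share nearer 20% would cost much power, and the documents give no reason to expect one. The dilution figures rest on assumed values of f and of the benefit in these patients. The possibility of entry at subscore 0–1 rests on the assumed four-item structure of the score.

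**What to change.** Add to inclusion criterion 4 that the Mayo endoscopic subscore must be at least 2 at the V0/V1 rectosigmoidoscopy, scored before randomisation. The examination and the score are already scheduled, and a total that includes the endoscopic item has to be known before criterion 4 can be applied. The cost is a few more screen failures and a protocol amendment with the reviews set out in sections 15.I and 16.III.

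If patients are already enrolled, exclude none of them. Keep the ITT analysis of section 12.I as the primary one, and specify, before outcome data are examined, a supportive analysis of the primary endpoint restricted to a baseline subscore of 2 or more. The subscore is measured before treatment, so the randomised comparison within that subset is preserved. Report the number with baseline subscore 0–1 by arm, which would supply the missing f. The restricted analysis helps interpretation; as step 6 shows, it should not be relied on to restore power.

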9. TREATMENT OF SUBJECTS

I) Treatment Definition

Treatment Groups:

- **Intravenous Bolus Group:** Intravenous methylprednisolone at a dose of 0.5 g/day for 3 consecutive days, followed by oral prednisone at 60 mg/day for one week, then a tapering regimen (reduction of 10 mg per week until reaching a dose of 20 mg, followed by a reduction of 5 mg per week until complete discontinuation).
- **Oral Prednisone Group:** Oral prednisone at a dose of 60 mg/day for one week, followed by a tapering regimen (reduction of 10 mg per week until reaching a dose of 20 mg, followed by a reduction of 5 mg per week).

II) Concomitant Treatments

For both treatment groups, the following concomitant treatments are recommended:

- **5-ASA Suppositories:** 1g/day for the first four weeks.
- **Calcium and Vitamin D Supplementation:** Calcium at 1000 mg/day and Vitamin D at 800 IU/day until corticosteroids are discontinued.
- **Maintenance Therapy with Mesalazine:** 2-2.4 g/day after prednisone dose tapering to 20 mg/day (patients on 5-ASA at the time of flare-up will discontinue it at the study's inclusion and continue with mesalazine until the end of the study). Dosage modifications can be made at the investigator's discretion and documented in the data collection notebook.

Any other concomitant treatment that the patient receives during the study must be documented in the e-CRD.

III) Contraceptive Methods

Acceptable contraceptive methods for women of childbearing potential participating in the study include barrier methods (diaphragm or condom), intrauterine devices (IUDs), or sexual abstinence during the entire study duration.

Women using hormonal contraceptives as their usual method of birth control must choose an additional method from those described above, as the metabolism of hormonal contraceptives through cytochrome P450 CYP3A4 may be affected by corticosteroid treatment.

IV) Procedures for Monitoring Subject Adherence

Intravenous methylprednisolone boluses will be administered by nursing staff. Oral medication will be prescribed as per usual clinical practice by the principal investigator or a delegated individual.

Nursing staff responsible for intravenous administration must:

- Shake the medication well to obtain a white, slightly opaque suspension.
- Visually inspect the medication before and after reconstitution for any foreign particles and/or physical changes.

- Not use the medication if there are any changes in appearance or if it has been frozen.
- Administer the medication immediately after preparation.

10. EFFICACY EVALUATION

I) Specification of Efficacy Parameters

Treatment will be considered effective if the patient achieves clinical and endoscopic remission, steroid-free, at 8 weeks and up to 54 weeks, without requiring rescue treatment or corticosteroids.

The parameters used to measure efficacy will include clinical remission, endoscopic remission, and the need for corticosteroids or other rescue treatments.

II) Methods and Schedule for the Evaluation, Recording, and Analysis of Efficacy Parameters

i) Local Determinations

In the Laboratory:

Blood tests for hematological and biochemical values will be performed per usual clinical practice in each participating center.

Hematological parameters: hemoglobin, hematocrit, platelets, white blood cells, and differential leukocyte count.

Biochemical parameters: GOT, GPT, alkaline phosphatase, GGT, total bilirubin, creatinine, urea, sodium, potassium, glucose, cholesterol, triglycerides, albumin, and C-reactive protein.

Baseline stool culture.

Pregnancy test for women of childbearing potential without sterilization.

In the Endoscopy Unit:

Rectosigmoidoscopies will be performed at inclusion, at 8 weeks, and at 54 weeks.

- Prior rectal and sigmoid cleansing should be conducted per the investigator's discretion and standard clinical practice at each center.
- The procedure may be performed with or without sedation as per the guidelines of each Endoscopy Unit.

ii) Central Laboratory Determinations

During Visit 0 or 1, before administering the first corticosteroid dose, a 10 ml blood sample will be collected in an EDTA tube to validate corticosteroid response predictive markers. The sample will be sent at room temperature to the Biobank of the Institut d'Investigació en Ciències de la Salut Germans Trias i Pujol (IGTP), located at [name].

During Visits (V1-V8), fecal samples will be obtained for centralized determination of fecal calprotectin levels, with results blinded to the treating physician.

11. SAFETY EVALUATION

Safety evaluations will be conducted in accordance with GCP standards and applicable regulations. The sponsor has delegated management of adverse events (AEs) recorded during the study to the Spanish Clinical Research Network (SCReN), responsible for notifying regulatory authorities (AEMPS, regional health authorities) and CEIm of serious and unexpected adverse reactions (SUSARs), annual reports, or other relevant safety information.

I) Specification of Safety Parameters

Adverse Event (AE)

Any harmful incidence affecting the health of a patient or clinical trial subject treated with a medication, whether or not it has a causal relationship with the medication.

Adverse Reaction (AR)

Any harmful and unintended response to a medication. It refers to any harmful and unintended response to a medication, regardless of the dose administered.

Serious Adverse Reaction (SAR) / Serious Adverse Event (SAE)

Adverse events or reactions are considered serious if, at any dose, they result in death, pose a threat to the life of the subject, require hospitalization or prolong an existing hospitalization, cause permanent or significant disability or incapacity, or lead to a congenital anomaly or malformation. For reporting purposes, any suspected AE or AR deemed medically important will also be treated as serious, even if they do not meet the previous criteria, such as those that threaten the patient or require intervention to prevent any of the aforementioned outcomes, and any suspected transmission of an infectious agent through a medication.

Levels of Intensity

- **Mild** - Transient, without activity limitation, no medical intervention/treatment required.
- **Moderate** - Some activity limitation, some assistance may be needed, requires minimal or no medical intervention/treatment.
- **Severe** - Marked activity limitation, usually requires some form of assistance, requires medical intervention/treatment, hospitalization may be necessary.

Causality Criteria

The sponsor will classify adverse events based on their causal relationship with the drug according to the Karch and Lasagna (1977) algorithm as:

- **Definitive:** There is a reasonable temporal sequence between the administration of the drug and the occurrence of the AE. This event matches the ARs described

for the drug, improves with discontinuation of the drug, reappears upon re-administration, and cannot be explained by alternative causes.

- **Probable:** There is a reasonable temporal sequence between the administration of the drug and the occurrence of the AE. This event matches the ARs described for the drug, improves after treatment is interrupted, and cannot be explained by other alternatives.
- **Possible:** There is a reasonable temporal sequence between the administration of the drug and the occurrence of the AE. This event matches the ARs described for the drug but may be explained by alternative causes.
- **Conditional or Unlikely:** There is a reasonable temporal sequence between the administration of the drug and the occurrence of the AE. This event does not match the ARs described for the drug and may be explained by alternative causes.
- **Unrelated:** There is no reasonable temporal sequence between the administration of the drug and the occurrence of the AE. This event does not match the ARs described for the drug and may be explained by alternative causes.

For expeditious reporting, the categories "definitive," "probable," and "possible" from the Karch and Lasagna (1977) algorithm will be considered related, and the category "conditional or unlikely" will be considered unrelated.

Determining the potential relationship to the study treatment is the responsibility of the principal investigator at the research site or the person designated by them.

Serious Adverse Event (SAE)

Any harmful incident affecting the health of a subject that, at any dose:

- Requires hospitalization or prolongation of hospitalization,
- Causes permanent or significant disability or incapacity,
- Leads to a congenital anomaly or malformation,
- Poses a threat to life or results in death,
- Is considered medically significant.

For reporting purposes, any suspected AE or AR deemed medically important will also be treated as serious, even if they do not meet the previous criteria, including medical events requiring intervention to prevent any of the aforementioned outcomes. Any suspected transmission of an infectious agent via a medication will also be considered serious.

The term "life-threatening" refers to the investigator's opinion that the patient is at real risk of death at the time of the AE or AR; it does not refer to the hypothetical possibility that the AE/AR could have led to death if it had been more severe.

It should not be confused with the term "severe," which refers to the intensity of the AE or AR (mild/moderate/severe).

Serious and Unexpected Adverse Reaction (SUSAR)

A serious adverse reaction whose nature, severity, or outcome is inconsistent with the reference safety information. In this case, the product information (SmPC) will be used as the reference.

SAEs that meet the SUSAR criteria and are associated with blinded studies should be reported to Health Authorities with the open-label unblinding.

Adverse Events of Special Interest in this Study

Infections, events that lead to the discontinuation of the study treatment, and the development of diabetes mellitus or hypertension are considered of special interest.

Expected Adverse Reactions Not Clinically Significant in this Study

The following adverse reactions are commonly associated with the study medication in clinical practice. They will be recorded in the patient's medical history, but for reporting purposes, they will not be collected in the e-CRF unless, in the investigator's clinical judgment, they meet the severity criteria.

These include the occurrence of hirsutism, moon face, acne, insomnia, weight gain, buffalo hump, and stretch marks.

II) Methods and Schedule for Evaluation, Recording, and Analysis of Safety Parameters

Adverse events will be recorded from the administration of the study drug until the end of the patient's participation in the study, whether spontaneously reported by the patient or detected during study visits.

Follow-up of all ARs, SAEs, and SAREs will be conducted until resolution, irreversibility, or study completion, whichever occurs first.

All ARs, SAEs, SAREs must be documented in the patient's medical history and in the e-CRF, except for clinically insignificant ARs described above.

Any pregnancy occurring during the study and its outcome must be recorded and followed to rule out congenital anomalies or malformations. Information will be gathered on:

- Normal birth, spontaneous or therapeutic abortion (any congenital anomaly detected in the aborted fetus should be documented), stillbirth, congenital anomaly.
- Neonatal deaths within 30 days of birth.
- Infant death after 30 days if the investigator suspects it is related to in-utero exposure to the study medication.
- All infants born after fetal exposure must be followed during the first 12 months after delivery.

Any exacerbation of a pre-existing disease occurring after the start of the study treatment is also considered an adverse event.

Any abnormal result in laboratory tests that the investigator considers clinically significant and requires dose adjustment, temporary or permanent interruption of the study treatment, or any type of intervention or diagnostic evaluation to assess the risk to the patient, will be recorded as an adverse event and must be properly investigated and monitored.

In the case of an SAE that must be reported to the Pharmacovigilance Unit, or a pregnancy case, a member of the investigator team will complete and sign the SAE or pregnancy notification form (see Annexes 5 and 6) and send it via fax immediately, and

within 24 hours of knowledge of the event, to:

[name] / [name]
UICEC, Hospital Universitario de Canarias
[contact]
[contact]

The Pharmacovigilance Unit will review the received form and, if necessary, will request additional information from the investigator.

Once additional information is obtained on the SAE/pregnancy, or the event is resolved or unlikely to change, a follow-up report should be completed and sent, via fax, to the Pharmacovigilance Unit.

Any SAE should be reported within 30 days of the last dose of medication (without time limit) if the investigator considers the SAE related to the study treatment (i.e., if it is an SARE) or if it is medically important.

The Pharmacovigilance Unit is responsible for reporting to the AEMPS (Clinical Trials Area of the Subdirectorate General of Human Medicines) and the Ethics Committee all SAREs that occur in the study, following the procedure established by current legislation.

III) Procedures for Obtaining Reports on Adverse Events and Intercurrent Diseases and for Recording and Communicating Them

The maximum reporting period for a suspected SARE case will be 15 calendar days from the moment the sponsor becomes aware of it.

If the suspected SARE has caused the death of the patient or put their life in danger, the sponsor will send the information within 7 calendar days from when they become aware of it and will complete the information, if possible, within the next 8 days.

Annual safety reports, including SAREs and SAEs recorded in the study, will be sent to the AEMPS (Clinical Trials Area of the Subdirectorate General of Human Medicines) and the Ethics Committee within the timeframes established by current legislation.

The project manager will communicate any safety information that could affect the safety of study subjects to the investigators as soon as possible.

SARE information will be sent annually, in aggregate form, with a brief analysis of the data provided.

Throughout the study, investigators will be informed of any safety aspects that affect the conduct of the clinical trial or protocol amendments related to safety.

IV) Type and Duration of Follow-up of Subjects After Adverse Events

If a patient experiences any disease or adverse event during the study that, by itself or due to requiring pharmacological treatment, may alter the disposition of any of the study drugs or make its administration unadvisable, the patient will be excluded from the study, and the cause will be detailed. If the adverse reaction is mild or moderate, requires treatment or not, and does not lead to discontinuation of the drug, the reaction will be detailed, and the study will proceed as planned.

Notification

Report on the corresponding data collection form (Annex 5).

